The presence of postincisional hernia need to be considerate as a serious disease, insomuch as it carry on highs rates of morbimortality. The presence of this eventuality is among 0.4-1.2% in elective

surgery and up to 30% in emergency procedures.

It is calculated in de U.S.A. an approximate of 1 million of reinterventions a year to correct this condition, with the respective monetary, time and suffering cost to the patient and the health system.

Given the seriousness, the ultimate global consensus has determinate three main axes to the surgical community to board:

- Identify the relevance of the problem
- Improve the theoretical knowledge and technical capacity in the closing of the abdominal wall
- Implement prophylactic measures in the patients, especially in those with elevated risk.

With the present study we aim to contribute to this global recommendations, comparing two closing techniques of the abdominal wall after a midline laparotomy in patients with elevated risk of herniation. Both techniques are proved safe and useful in other studies, with no comparison to date.

Demonstrate that the use of RTL technique has a similar incidence of herniation than the mesh, in an attempt to prevent postincisional hernias after a midline laparotomy, will bring to the surgical community a cheaper and practical alternative to the mesh.

Objectives:

General:

To determinate if the incidence of post-incisional hernia in patients with high risk after a midline laparotomy are similar between the closure of the abdominal wall with the RTL technique and the supraaponeurotic mesh closure reinforcement.

Specifics:

- To identify the patients with high risk using de validated HERNIA-Project Score.
- To determinate the incidence of post-incisional hernia after one year of the initial midline laparotomy.
- To compare the incidence of post-incisional hernia between the two groups.
- To describe the complications related to each closure technique.

Hypothesis:

Ho Hypothesis:

There is no difference in the incidence of post-incisional hernia between the RTL technique and the reinforcement with supraaponeurotic mesh closure wall.

H1 Hypothesis:

There is difference in the incidence of post-incisional hernia between the RTL technique and the reinforcement with supraaponeurotic mesh closure wall.

Sample size:

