The sample size was calculated according to the formula published by Bouemn et all 2015, and based on the results of Kholer and collaborators 2019, where they found in which a percentage of

success was estimated with the standard treatment of 18.5% compared to the experimental management of 7.2%, with a margin of no less than 3%, with an alpha for a tail of 0.05%, and a beta of 20 %, with a percentage of estimated losses of approximately 10%, a total of 195 patients per group was obtained.

Statistical analysis Data are presented as frequency and percentage, comparisons between groups were using the χ^2 test for binary data or Fisher's exact test. Continuous variables are presented as median and range interquartile range and were compared using the Mann-Whitney U-test or t student test if they meet normal criteria. p-Values of less than 0.05 were considered significant. Statistical analyses were performed with SPSS version 25.0.0. Analysis by intention to treat was used.

Study Type:	Interventional
Primary Purpose:	Treatment
Study Phase:	Phase 4
Interventional Study Model:	Parallel Assignment
	Clinical trial of non-inferiority
Number of Arms:	2
Masking:	Triple (Participant, Care Provider, Investigator)
Allocation:	Randomized
Enrollment:	390 [Anticipated]

Primary Outcome Measure:

1. Incisional Hernia

any abdominal wall gap with or without bulge in the area of a postoperative scar perceptible or palpable by clinical examination

[Time Frame: 12 and 24 months]

Secondary Outcome Measures:

2. postoperative complications

an undesirable and unintended result of an operation affecting the patient that occurs as a direct result of the operation. Haematoma, Facial dehiscence, mesh removal, ileus, reinterventions, re-admissions and death

[Time Frame: 1 month, 1 and 2 years]

Elegibility:

Minimum Age:	18 Years
Maximum Age:	70 Years
Sex:	All
Gender Based:	No

Accepts Healthy Volunteers: Yes

Criteria:

Inclusion Criteria:

- Patients older than 18 years undergoing midline laparotomy, independently of diagnostic or condition, elective or emergency surgery
- Patients with a score equal or greater than 7 of the hernia score
- Patients who accept to participate and sign the informed consent

Exclusion Criteria:

- Patients managed with open abdomen or with the impossibility of close the wall
- Patients who had a previous incisional hernia or patients who are participating in another trial
- Patients with a life expectative less than 12 months

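### The sample size paragraph prints a one-tail alpha of 0.05%, but 195 per group comes from one-sided 5%, and the analysis section uses neither that level nor a test against the margin

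*Combined protocol and SAP*

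**What the plan says.** The Sample size section calculates the number of patients "with an alpha for a tail of 0.05", the figure being printed with a percent sign, "and a beta of 20" percent. The rates are given as "success was estimated with the standard treatment of 18.5% compared to the experimental management of 7.2" percent, "with a margin of no less than 3" percent, and losses are put at about 10%. The result is "a total of 195 patients per group was obtained". The design table that follows gives a non-inferiority trial with two parallel arms and 390 patients.

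The Statistical analysis section says that "comparisons between groups were using the χ^2 test for binary data", or Fisher's exact test, and that "p-Values of less than 0.05 were considered significant". It gives no sidedness, no confidence interval and no mention of the margin.

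The Hypothesis section words H1 without direction: "There is difference in the incidence of post-incisional hernia between the RTL technique" and mesh reinforcement.

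No section states a one-sided 5% level or says which level governs the non-inferiority conclusion.

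**The concern.** In a non-inferiority trial the one-sided error level, together with the margin, decides the primary conclusion. Here the level printed beside the sample size cannot be the one that produced it. The only threshold in the analysis section belongs to a different kind of test. A reader cannot tell from the plan at what level non-inferiority would be declared, and the choice could be made after the data are seen.

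**Working it through.** **Inputs** (Sample size section): rates 0.185 and 0.072; margin 0.03; beta 0.20, so z = 0.8416; stated result 195 per group. The formula is taken from a cited paper that is not among the documents, so the standard unpooled form is assumed.

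**1. Reproducing 195.**
- Variance term: 0.185 × 0.815 + 0.072 × 0.928 = 0.1508 + 0.0668 = 0.2176.
- Difference: 0.185 − 0.072 = 0.113. Distance with the margin subtracted: 0.113 − 0.03 = 0.083.
- n per group = (z_alpha + 0.8416)² × 0.2176 / 0.083².
- At one-sided 5%: (1.6449 + 0.8416)² × 0.2176 / 0.006889 = 195.3. This is the stated figure, before losses. Rounded up to 196 and divided by 0.9, it becomes 218.

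**2. The alpha as printed.** At one-sided 0.05% (0.0005): (3.2905 + 0.8416)² × 0.2176 / 0.006889 = 539.3. The printed alpha does not give the printed number.

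**3. Other routes to 195.**
- With the margin added to the difference (0.113 + 0.03 = 0.143), one-sided 0.05% gives 181.7, or 203 with losses (182 / 0.9). Neither is 195.
- A two-sided 0.05% level at 0.143 gives 198.8 before losses. This is close, but it contradicts the plan's own statement that alpha is for one tail.
- Pooled variance, equal rates in the two arms, and superiority formulas with and without continuity correction were also tried. None gave a better match than step 1.

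**4. The level in the analysis section.** A chi-square test at p<0.05 with a non-directional H1 is a two-sided 5% test of zero difference, which is 2.5% in each direction. Its power at 195 per group for 18.5% against 7.2%:
- Mean rate 0.1285; null standard error √(2 × 0.1285 × 0.8715 / 195) = 0.03389; critical difference 1.96 × 0.03389 = 0.0664.
- Standard error under the alternative √(0.2176 / 195) = 0.0334.
- (0.113 − 0.0664) / 0.0334 = 1.39, so power is 91.8%. This is not the stated 80%, and the test does not address the margin.

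**5. Why the 80% does not belong to a margin-based rule for hernia.** Suppose 7.2% is the RTL hernia rate and 18.5% the mesh hernia rate, and the rule is that the upper limit for RTL minus mesh lies below +3 points. The true difference is then −11.3 points and the distance to the margin is 14.3 points.
- One-sided 5%: 0.143 / 0.0334 − 1.645 = 2.64, power 99.6%.
- One-sided 2.5%: 0.143 / 0.0334 − 1.960 = 2.32, power 99.0%.
- If the rates are taken literally as success, RTL is 11.3 points worse, which is 8.3 points beyond the margin, and power is near zero.

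**6. What the choice of level changes.** For illustration, assume about 7.2% hernia in both arms, 195 per group and a normal approximation. The standard error is √(2 × 0.0668 / 195) = 0.0262.
- A 90% interval clears +3 points if the observed difference is at or below 3 − 1.645 × 2.62 = −1.3 points.
- A 95% interval needs 3 − 1.96 × 2.62 = −2.1 points.
- At 18.5% in both arms the corresponding values are −3.5 and −4.7 points.

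**The case against.** The strongest reply is that 0.05% is an obvious slip for 0.05. The reproduction of 195 at 5% supports this, and so does the 0.05 threshold in the analysis section. This stands: no one is likely to have sized or planned to test the trial at 0.05%. Correcting the slip still leaves a one-tailed design level beside an analysis rule that has no stated side and no margin.

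It is also fair to say that the documents never call the tests two-sided. That is inferred from the chi-square test and the non-directional H1. The match to 195 is itself a back-calculation: it depends on the 8.3-point distance and on leaving out the losses that the text says are included.

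A reader might go further and infer that three error levels compete for one decision, or that the trial really has 70% power (at one-sided 2.5%) or 21% (at 0.05%). The documents do not support this. Those powers take the 8.3-point distance with a margin-based test, and the plan contains no such test. The p<0.05 rule governs tests of zero difference.

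**Conclusion.** The point holds in this form. The printed one-tail alpha of 0.05% is wrong: with the plan's own inputs it corresponds to 539 per group, against 195.3 at one-sided 5%. The analysis section does not carry the one-sided design level through. As written, it implies two-sided testing of zero difference.

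This is more than a clerical slip, because the error level for the primary conclusion is left undefined. In the illustration above, the choice between one-sided 5% and 2.5% moves the result needed for non-inferiority by about 0.8 to 1.2 points. The conclusion rests on the unpooled formula with the 8.3-point distance as the source of 195, and on the inferred sidedness of the analysis tests. It does not establish that the trial is underpowered. The direction of the rates, the omitted losses and the missing margin-based test are separate defects, and the power cannot be stated correctly until they are settled.

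**What to change.** - In the Sample size section, replace the printed alpha with 5% (0.05), one-sided.
- In the Statistical analysis section, state that the primary non-inferiority decision uses that level: the upper limit of the two-sided 90% confidence interval for RTL-minus-mesh hernia incidence must lie below the 3-point margin.
- State that two-sided p<0.05 applies to the other comparisons.
- Do not attach 80%, 70% or 21% power to this rule. Restate power once the direction of the rates and the treatment of losses have been corrected.
- If the sponsor prefers a two-sided 5% primary level (95% interval), say so and restate the power for that level on the same corrected basis.

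The change to the level and the decision rule is wording only and in itself needs no more patients. The restated power calls for a short recalculation. The change should be made before outcome data are compared between groups.

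### The stated inputs give 195 per group before losses, not after: with the planned 10% allowance the same calculation gives 215 to 217

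*Combined protocol and SAP*

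**What the plan says.** The Sample size section of the combined protocol and SAP gives one sentence of inputs and one result.

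- Method: "The sample size was calculated according to the formula published by" a 2015 paper in the reference list. The formula is not printed.
- Rates and margin: "success was estimated with the standard treatment of 18.5% compared to the experimental management of 7.2%, with a margin of no less than 3" percent.
- Error rates: "with an alpha for a tail of 0.05%, and a beta of 20" percent.
- Losses and result: "with a percentage of estimated losses of approximately 10%, a total of 195 patients per group was obtained".

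The study design table labels the trial "Clinical trial of non-inferiority" and gives enrolment as "390 [Anticipated", in square brackets. Nothing is added after the 195. The Statistical analysis paragraph states "p-Values of less than 0.05 were considered significant" and "Analysis by intention to treat was used". It gives no rule for patients without an outcome. No pre-loss number and no inflation step appear anywhere.

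**The concern.** The wording presents 195 as the result after the loss allowance. If it is in fact the number before losses, the trial has no allowance at all within its own calculation. About 10% of each group could then go without the 12- and 24-month examination on which the primary outcome depends, and the stated 80% power would not hold for the patients who remain. The reader of the eventual report would also be told that attrition had been planned for when it had not.

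**Working it through.** **Inputs, all from the Sample size section.** p1 = 0.185 (standard), p2 = 0.072 (experimental), margin 0.03 read as 3 percentage points, beta 0.20, losses 10%, equal groups. Alpha is one-sided and read as 0.05. The text prints 0.05%, but the 0.05 significance threshold in the Statistical analysis paragraph supports this reading.

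**Reproducing 195.** Unpooled formula: n = (z_alpha + z_beta)² × [p1(1−p1) + p2(1−p2)] / distance².

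- Variance term: 0.185 × 0.815 + 0.072 × 0.928 = 0.150775 + 0.066816 = 0.217591.
- (1.6449 + 0.8416)² = 6.1826.
- Distance: (0.185 − 0.072) − 0.03 = 0.083, squared 0.006889.
- n = 6.1826 × 0.217591 / 0.006889 = 195.28 per group.

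Strict rounding up gives 196. With z values rounded to 1.64 and 0.84 the result is 194.3, which rounds up to 195; with 1.645 and 0.84 it is 195.0. So 195 is reproduced, with no loss allowance in it.

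**Adding the stated losses.** 195.28 × 1.1 = 214.8, so 215. 195.28 / 0.9 = 217.0, so 217. The gap from 195 is 20 to 22 per group.

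**Other routes to 195.** I varied one-sided alpha (0.05, 0.025, 0.0005, 0.00025), distance (8.3, 14.3 or 11.3 points), variance (unpooled, pooled, mixed, 7.2% in both arms, 18.5% in both arms), continuity correction (with or without) and losses (none, ×1.1, ÷0.9). Five of the 360 combinations fall within one patient of 195:

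| One-sided alpha | Distance | Variance | Continuity correction | Losses | n per group |
|---|---|---|---|---|---|
| 0.05 | 8.3 | unpooled | no | none | 195.28 |
| 0.0005 (as printed) | 14.3 | unpooled | yes | none | 195.42 |
| 0.00025 | 11.3 (no margin) | 7.2% both arms | no | none | 195.52 |
| 0.0005 | 11.3 (no margin) | 7.2% both arms | yes | none | 195.99 |
| 0.025 | 8.3 | 7.2% both arms | yes | ÷0.9 | 195.02 |

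Only the last includes losses. It needs an alpha of 0.025 and a variance that ignores the 18.5%, neither of which the text states. Alpha as printed, with distance 14.3 and no continuity correction, gives 199.9 (×1.1) or 201.9 (÷0.9): near 195, but not equal to it.

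**Power after losses.** 195 × 0.9 = 175.5 per group. Power = Φ(distance / √(0.217591/n) − 1.6449).

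- n = 195: 0.083 / 0.033404 − 1.6449 = 0.840, power 80.0%.
- n = 175.5: 0.083 / 0.035211 − 1.6449 = 0.712, power 76.2%.

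**What this power is not.** The 8.3-point distance is not that of the declared non-inferiority test. At 175.5 per group and one-sided 0.05, the power of that test depends on what the rates mean:

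- Hernia rates, with the reinforced tension line (RTL) closure truly 11.3 points better: distance 0.143, 0.143 / 0.035211 − 1.6449 = 2.416, power 99.2%.
- Literal success rates, with RTL 11.3 points worse: distance −0.083, power below 0.01%.
- Equal rates (my assumption), 7.2% in both arms: 0.03 / √(0.133632/175.5) − 1.6449 = −0.558, power about 29%.
- Equal rates (my assumption), 18.5% in both arms: 0.03 / √(0.30155/175.5) − 1.6449 = −0.921, power about 18%.

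**The case against.** The strongest reply is that the formula cannot be seen. One version of it was inferred because it lands on 195, and it needs the printed alpha to be re-read. On this view the documents show only that the loss step is not displayed, not that it was left out. That stands as a limit on certainty: a reader might infer that the omission is proven, and it is not. It does not remove the point. The most direct use of the stated inputs gives 195 before losses, and the only match within one patient that includes losses rests on inputs the text does not state.

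A second reply is that intention to treat keeps everyone in the analysis, so no power is lost. The plan names the principle but gives no rule for a missing hernia outcome, so the drop to 175 remains an assumption rather than a fact.

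A third reply is that nothing is at stake, because on hernia rates the non-inferiority test has about 99% power even at 175 per group. That figure holds only if RTL truly has 11.3 points fewer hernias than mesh. The general objective looks for similar incidence, and the Justification says the two techniques have not been compared. At equal rates the power is about 29% or 18%, so the 99% is no reassurance.

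**Conclusion.** The point holds as a reconstruction. With alpha read as one-sided 0.05, unpooled variance and an 8.3-point distance, 195 is the number before losses, and the same inputs with the stated 10% give 215 to 217. If 10% leave the analysis, the power of that calculation is about 76% rather than 80%.

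A reader might infer that the trial must recruit 217 per group. The documents do not support this. The 8.3-point distance does not describe the declared test, and no sample size can be called right until it is settled whether 18.5% and 7.2% are hernia or success rates and which way the margin runs. The supported conclusion is narrower: the stated number does not contain the allowance it is said to contain, and the text should be corrected.

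**What to change.** Keep enrolment at 390. Retrieve the original calculation and state the formula, the alpha, the number before losses and how the 10% was applied. Unless that record shows that losses were included, describe 195 per group as the number before losses, with about 175 per group evaluable at 10% loss and about 76% power for that calculation. Write alpha as one-sided 0.05 if that is what was used.

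Do not replace the 80% with about 99%. State a power for the non-inferiority test only after the meaning of the two rates and the direction of the margin are settled, and include the equal-rates case alongside it.

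The cost is a few corrected sentences and one recalculation. Enrolment and conduct do not change. The downside is a less favourable stated power.

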- Pregnant patients Patients with the antecedent of rejection of prosthetic material

Revised Hernia Score.

$$\text{Revised HERNIA score} = 1 \times (\text{BMI} \geq 25 \text{ kg/m}^2) + (1 \text{ COPD}) + (5 \times \text{extended laparoscopy}) + (6 \times \text{laparotomy}) + (3 \times \text{earlier abdominal operation})$$

The revised HERNIA score was developed and low risk was assigned 0 to 6.9 points, medium risk was assigned 7.0 to 9 points, and high risk was assigned ≥ 9 points.

[figure not shown]
Arms and interventions:

Active Comparator: Onlay Mesh Reinforcement group

The midline fascia was closed with running, slowly absorbable sutures (PDS 1-0) with a recommended suture length to wound length ratio of 4:1. An anterior plane with a width of about 8 cm was created between the anterior fascia and the subcutis. A Lightweight polypropylene mesh was used and placed on the anterior rectus fascia with an overlap of 3 cm. The mesh was fitted in the dissected space and it was fixed with PDS 2-0 suture. Fixing points are placed taking the mesh and the anterior fascia of the rectus muscle, at a distance of 3 cm between each point until completing its circumference.

Experimental: RTL reinforcement group

The RTL suture is placed parallel at a distance of 0.5 cm from the fascial margin. Ideally the thread should lie between the anterior and the posterior rectus muscle sheath; there should be no contact with the rectus muscle. A nonabsorbable monofilament polypropylene thread and a 65-mm $\frac{1}{2}$ needle are used. Around this longitudinal thread, the continuous suture for fascial closure is introduced immediately lateral to the thread; with running, slowly absorbable sutures (PDS 1-0) with a recommended suture length to wound length ratio of 4:1. An anterior plane with a width of about 8 cm was created between the anterior fascia and the subcutis.

References

- Shell DH 4th, de la Torre J, Andrades P, Vasconez LO. Open repair of ventral incisional hernias. Surg Clin North Am. 2008 Feb;88(1):61-83, viii. doi: 10.1016/j.suc.2007.10.008. Review. PubMed ID: 18267162

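### The primary outcome has only unadjusted tests and no interval to set against the 3-point margin; a risk difference stratified on entry score or urgency is a cheap but small improvement

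*Combined protocol and SAP*

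**What the plan says.** The statistical analysis paragraph has one rule for binary data: "comparisons between groups were using the χ^2 test for binary data" or Fisher's exact test. Incisional hernia is binary, so this rule covers the primary outcome. No covariate, stratified analysis or stratification factor for randomisation is named. No risk difference or confidence interval is named either.

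The non-inferiority quantities appear only in the sample-size paragraph: "success was estimated with the standard treatment of 18.5% compared to the experimental management of 7.2%, with a margin of no less than 3" per cent, "with an alpha for a tail of 0.05" (also printed with a per cent sign), 80% power and about 10% losses, giving 195 per group.

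Two baseline factors in the documents bear on hernia risk:

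- **Urgency.** The Inclusion Criteria admit patients "independently of diagnostic or condition, elective or emergency surgery". The Justification gives background figures: "The presence of this eventuality is among 0.4-1.2% in elective" "surgery and up to 30% in emergency procedures".
- **Entry score.** The Inclusion Criteria require "Patients with a score equal or greater than 7 of the hernia score". The Revised Hernia Score gives 6 points for laparotomy, 1 for BMI of 25 or more, 1 for COPD and 3 for "earlier abdominal operation". It has no term for urgency.

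**The concern.** The plan calls the trial non-inferiority, but a chi-square or Fisher p-value tests for a difference and cannot be read against a 3-point margin. An interval for the risk difference has to be written into the plan in any case. When it is, leaving it unadjusted would ignore risk information that is known before the closure is done. If a stratification factor is prognostic, the interval narrows with no added patients. If it is not, almost nothing is lost. The stake is efficiency only: randomisation already makes the unadjusted comparison valid.

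**Working it through.** **Inputs.** From the sample-size paragraph: 18.5% and 7.2% (labelled as success, read here as hernia rates), margin 3 points (read as absolute), alpha 5% one-sided (printed as 0.05%), 80% power, 195 per arm, 10% losses. From the Justification: 0.4-1.2% elective, up to 30% emergency. Not in the documents, and therefore assumed: the emergency share and the stratum risks in patients scoring 7 or more with reinforced closure.

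**1. The plan's own figure.** (1.645 + 0.842)² × (0.185×0.815 + 0.072×0.928) / (0.113 − 0.03)² = 195.3. The stated 195 therefore reproduces, before any allowance for losses, with alpha 5% one-sided and an absolute margin. An alpha of literally 0.05% would give 540. This supports the two readings, but the sponsor should confirm them.

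**2. Unadjusted precision.** Evaluable per arm: 195 × 0.9 = 175.5, taken as 175. Overall rate p = (18.5 + 7.2)/2 = 12.85%, so p(1−p) = 0.1120. At equal risks:

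- standard error = √(2 × 0.1120/175) = 3.58 points
- one-sided half-width = 1.645 × 3.58 = 5.88 points
- power = Φ(3/3.58 − 1.645) = 21.0%

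**3. Gain from two strata.** With stratum risks p1 < p2 and overall rate p, the share in the higher-risk stratum is f = (p − p1)/(p2 − p1), and the proportional cut in variance is (p − p1)(p2 − p)/[p(1 − p)]. For 5% versus 20%: 0.0785 × 0.0715/0.1120 = 5.0%.

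| Elective vs emergency risk | f | Variance cut | Half-width (points) | Power |
|---|---|---|---|---|
| 10% vs 15% | 0.57 | 0.5% | 5.87 | 21.1% |
| 10% vs 20% | 0.29 | 1.8% | 5.83 | 21.2% |
| 1.2% vs 15% | 0.84 | 2.2% | 5.82 | 21.3% |
| 0.4% vs 15% | 0.85 | 2.4% | 5.81 | 21.3% |
| 5% vs 20% | 0.52 | 5.0% | 5.74 | 21.6% |
| 1.2% vs 20% | 0.62 | 7.4% | 5.66 | 22.0% |
| 0.4% vs 20% | 0.64 | 7.9% | 5.65 | 22.0% |
| 5% vs 30% | 0.31 | 12.0% | 5.52 | 22.6% |
| 1.2% vs 30% | 0.40 | 17.8% | 5.33 | 23.6% |
| 0.4% vs 30% | 0.42 | 19.1% | 5.29 | 23.8% |

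The last three rows need emergency risk to average the quoted maximum. The same formula serves for score category, with its two stratum risks in place of these, but the documents give no rates by score.

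**4. Simulation check** (200,000 trials per scenario, nine scenarios). Mantel-Haenszel variance cuts run 0.1-0.5 points below the formula. With equal stratum risks the result is a loss of 0.3%. At equal risks, coverage of the upper limit is 94.9-95.0% with Sato's variance and 94.8-94.9% unadjusted. At a true 3-point excess, the error is 5.1-5.2% with Sato's variance and 5.0-5.1% unadjusted.

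**5. Sparse elective stratum.** Expected elective hernias per arm = 175(1 − f)p1. At 0.4% vs 15%: 175 × 0.147 × 0.004 = 0.10. At 1.2% vs 30%: 175 × 0.596 × 0.012 = 1.25. In the simulated scenarios with 0.4-1.2% elective risk, 8-82% of trials had no elective hernia in either arm.

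**6. Score category.** Taking the extended-laparoscopy points as not added to the laparotomy points, a laparotomy patient without an earlier operation scores at most 6 + 1 + 1 = 8, and one with an earlier operation at least 6 + 3 = 9. Among eligible patients, 7-8 versus 9 or more is therefore the same split as no versus any earlier abdominal operation. The trial must already assess this for entry.

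**7. Sample size.** At equal risks, 80% power needs (1.645 + 0.842)² × 2 × 0.1120/0.03² = about 1,539 evaluable per arm. In the best row of the table it is still 1,539 × (1 − 0.191) = about 1,245.

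**The case against.** The strongest reply is that nothing here is an error: an unadjusted primary analysis is legitimate, and adjustment is a matter of preference. As regards validity, that stands. A reader might infer that the chi-square test is biased or invalid in this trial; randomisation rules that out. What goes beyond preference is that neither named test gives a limit to compare with the margin.

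It can also be said that there is no interval in the plan to stratify, so the point is a rider to a larger gap. That stands too, and it is why the change is framed as one clause of the missing analysis.

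A third reply is that the background figures do not describe these patients. This is right. A reader might infer from 0.4-1.2% against 30% that urgency is established as a strong predictor and that a variance cut near 19% is on offer. The documents do not support this. The 30% is a maximum, neither figure is for patients scoring 7 or more with mesh or RTL, and an elective risk near 1% is doubtful in patients selected for risk.

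Lastly, urgency is not the obvious covariate: the trial's own score omits it, and the documents do not list it as recorded, whereas the score category is determined at entry. This stands, so the score category is offered alongside urgency.

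**Conclusion.** The point holds as a low-priority improvement. The named tests are valid but use no baseline information and do not answer the non-inferiority question. For urgency, the expected gain is roughly 0.5-8% of the variance when the assumed emergency risk is 15-20%. It reaches 12-19% only if that risk averages the 30% ceiling, and about 0.3% is lost if urgency has no prognostic value. The gain from score category cannot be sized from the documents.

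These figures assume an overall hernia rate of 12.85%, 175 evaluable per arm, an absolute 3-point margin and one-sided 5% alpha. In the most favourable case (0.4% vs 30%), an overall rate of 7.2% would give a 23.2% cut and power from 28.8% to 34.2%; an overall rate of 18.5% would give 13.8% and power from 17.8% to 19.3%. No computed half-width falls to 3 points. A reader might hope that stratifying makes 195 per arm adequate; it does not. The missing non-inferiority interval and the shortage of patients both matter more.

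**What to change.** When the non-inferiority analysis is written, include the following:

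- Pre-specify the primary estimate as a Mantel-Haenszel risk difference, RTL minus mesh, and compare its one-sided 95% upper limit with the 3-point margin. Confirm that alpha is 5% one-sided and that the margin is absolute.
- Stratify by entry HERNIA score (7-8 versus 9 or more), by elective or emergency status recorded at baseline, or by both, keeping the strata few. State that a score of exactly 9 goes in the upper stratum, because the printed medium and high bands both contain 9.
- Name a variance that tolerates sparse strata, for example Sato's.
- Report the unadjusted difference as a sensitivity analysis.

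The cost is one clause and, if urgency is used, one baseline field. No patients or visits are added. The downside is a possibly sparse elective stratum: about 0.1-1.3 expected hernias per arm if elective risk is 0.4-1.2% and the overall rate 12.85%.
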